Intramuscular Heating Rates of a Chattanooga Intelect XT Therapeutic Ultrasound with a 3 MHz frequency and 1.0 W/cm² Intensity at Three Depths up to 2.5 cm.

1-22-19

Statistical Analysis Plan:

Twenty-five subjects will be recruited from the Institution's student population using the University email Listserv. Descriptive statistics will be utilized to determine the rate of increase for each depth. A 3×4 repeated measures ANOVA will be used to determine differences in temperature increases at 3 depths (1.0, 1.75 and 2.5 cm) at 4 different time points (baseline, 5,10,15 minutes). The level of significance will be set at $p \leq .05$

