6. Each thermocouple will be attached to the Iso Thermex electronic thermometer (Columbus Instruments, Columbus, OH), which will measure and record intramuscular temperatures from the tips of the thermocouples.
7. An ultrasound treatment template will be applied at the treatment site and secured with tape to maintain consistent treatment size.
  - a. This template will be twice the size of the transducer's Effective Radiating Area (ERA).

8. A metronome will be utilized to consistently move the transducer at a rate of 4 cm/s .
9. The ultrasound treatment will begin once the intramuscular temperature has remained the same for a minute.
10. Each subject will receive one ultrasound treatment at the following parameters: 3 MHz frequency, 1.0 W/cm^2 intensity, and 100% duty cycle using the Chattanooga Intelect® Legend XT.
  - a. Termination of treatment will result when any of the following occur:
    - i. A 15-minute treatment time is obtained.
    - ii. A 4°C temperature increase occurs at all three depths as this has been shown as the necessary temperature change to increase tissue extensibility.
    - iii. A 45°C temperature is reached at any depth, due to concern of tissue damage at high temperatures.
    - iv. The subject experiences any pain or discomfort during the treatment.
11. Following the treatment, the ultrasound gel will be wiped from the leg, the template and thermocouples will be removed, and the insertion sites will be cleaned with 70% isopropyl alcohol wipes and covered with a band aid.
12. The subject will then be instructed on the possibility of minor soreness for the next day or two and instructed on an icing schedule to decrease discomfort.

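### Treatment can stop early on the measured temperature, yet the SAP has no rule for subjects without 10- or 15-minute readings, and its 3×4 repeated measures ANOVA in the usual form would drop them

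*SAP*

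**What the plan says.** The SAP is one paragraph. It plans 25 subjects, descriptive statistics for the rate of increase at each depth, and one inferential analysis with two within-subject factors: "repeated measures ANOVA will be used to determine differences in temperature increases at 3 depths". In this 3×4 layout, depth (1.0, 1.75 and 2.5 cm) is crossed with time, and temperatures are compared "at 4 different time points (baseline, 5,10,15 minutes".

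The Protocol (Methods and Procedures Attachment, step 10.a) states: "Termination of treatment will result when any of the following occur". The four conditions are:

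- i. "A 15-minute treatment time is obtained"
- ii. "A 4°C temperature increase occurs at all three depths"
- iii. "A 45°C temperature is reached at any depth"
- iv. "The subject experiences any pain or discomfort during the treatment"

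Step 11 follows the end of treatment: "the template and thermocouples will be removed". Neither document mentions missing time points, carrying values forward, a mixed model, replacement of subjects, or how a rate is computed when treatment times differ.

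**The concern.** The Protocol foresees treatments shorter than 15 minutes, while the SAP assumes that every subject has a 15-minute reading. Conditions ii and iii are triggered by intramuscular temperature, which is the outcome analysed. Missing readings would therefore not be a random subset.

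A conventional two-way within-subject ANOVA uses only subjects with all 3 × 4 = 12 cells. A subject who stops at 13 minutes would be lost at every time point, including the 5- and 10-minute readings that were taken. Under condition ii a subject is lost only after the slowest depth has risen 4°C, so the remaining subjects' mean rise at that depth is too low. The depth comparison can be distorted as well. If the handling is chosen only after the data are in, it is chosen with the results in view.

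**Working it through.** **Inputs from the documents.** N = 25; readings at 0, 5, 10 and 15 minutes; stop at +4°C at all three depths or at 45°C at any depth; maximum 15 minutes. No heating rate, SD, baseline temperature, correlation between depths or checking interval is given, so there is no planned figure to reproduce.

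**Thresholds.** With linear heating and the 4°C stop applied as soon as it is met, a reading at time *t* is lost when the slowest depth heats faster than 4/*t*:

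- 15-minute reading: 4/15 = 0.267 °C/min
- 10-minute reading: 4/10 = 0.40 °C/min
- 5-minute reading: 4/5 = 0.80 °C/min

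If the rule is checked only once a minute, the first two become 4/14 = 0.286 and 4/9 = 0.444 °C/min. The 45°C stop removes the 15-minute reading when any depth exceeds (45 − baseline)/15. For an assumed baseline of 34 to 37°C that is 11/15 = 0.73 down to 8/15 = 0.53 °C/min.

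**Can the ANOVA run on incomplete subjects?** One standard routine (statsmodels AnovaRM) was given 25 subjects, one of them without 15-minute values. It stopped with an error that the data were unbalanced.

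**Size, by simulation.** All inputs here are assumptions: linear heating, baseline 35.5°C (SD 0.7), SD of the 15-minute rise 1.0°C at each depth, correlation 0.6 between depths, and mean rises at 1.75 and 1.0 cm that are 1 and 2°C above the 2.5 cm mean. Bias is the completers' mean 15-minute rise at 2.5 cm minus the mean had nobody stopped. Each cell gives checking continuously / checking each minute.

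| Mean 15-min rise at 2.5 cm | Complete, of 25 | Bias at 2.5 cm (°C) | Chance of at least one incomplete subject |
|---|---|---|---|
| 1.5°C | 24.9 / 25.0 | −0.01 / 0.00 | 8% / 3% |
| 2.5°C | 23.7 / 24.3 | −0.11 / −0.06 | 74% / about 50% |
| 3°C | 21.6 / 23.0 | −0.25 / −0.16 | 97% / 88% |
| 4°C | 13.1 / 15.9 | −0.75 / −0.57 | >99% / >99% |

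Under linear heating the 5-minute bias is 5/15 = one third of these values. Even at a 4°C rise, 24.6 / 24.9 of 25 subjects still have a 10-minute value, so nearly all the loss is at 15 minutes.

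**Sensitivity.**

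- *SD.* At a 3°C rise, SDs of 0.5, 1.0 and 1.5°C give bias −0.03, −0.25 and −0.49°C (continuous) or −0.01, −0.16 and −0.38°C (each minute).
- *Other depths, at a 4°C rise at 2.5 cm.* The bias at 1.0 cm is −0.48 / −0.37°C with correlation 0.6. It is +0.12 / +0.07°C if the correlation between 1.0 and 2.5 cm is −0.3 (1.0 with 1.75 cm −0.1, 1.75 with 2.5 cm 0.1).
- *Depth gap, same case.* The true gap between 1.0 and 2.5 cm is 2.00°C. Among completers it becomes 2.27 / 2.21°C in the base case, but 1.67 / 1.76°C if the SDs are 2.0, 1.5 and 1.0°C from shallow to deep.
- *45°C stop.* It hardly occurs in the base case. With a steeper assumed gradient (mean rises 9, 6 and 2°C; SD 1.5°C), about 38% of subjects would reach 45°C within 15 minutes. With continuous checking the completers' bias is then about −0.87°C at 1.0 cm and −0.60°C at 2.5 cm.

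**Does a mixed model help?** This used 300 simulated trials of 25 subjects per case, with records and checks each minute and noise SD 0.1°C. The true 15-minute rise at 2.5 cm was 4.00°C and the true gap 2.00°C. The model had depth × quadratic time, with random slopes for subject and subject-by-depth. Entries are the estimated rise (gap).

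| Case | Completers only | Quadratic mixed model |
|---|---|---|
| Correlation 0.6, linear | 3.42 (2.20) | 4.00 (1.99) |
| Correlation 0.6, flattening (time constant 10 min) | 3.33 (2.23) | 4.09 (1.88) |
| Shallow–deep correlation −0.3, linear | 3.62 (2.45) | 4.00 (2.01) |
| Shallow–deep correlation −0.3, flattening | 3.53 (2.58) | 4.00 (1.87) |

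A straight-line model in the second case gives 4.95. With a subject slope only, the quadratic model gives 3.91, 3.90, 3.87 and 3.69 in the four cases.

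**The case against.** - **Size is assumed.** Every number beyond the thresholds rests on inputs that the documents do not give, and the bias at 2.5 cm runs from 0.00 to −0.75°C. This stands. Only the missing rule is certain.
- **The SAP does not say that it will drop anyone.** It names no software or fitting method, and the failed run is one routine's behaviour. That is fair, but a classical repeated measures ANOVA needs complete cells, and the SAP offers no alternative.
- **The thresholds assume instant stopping.** True. Results for checking each minute are shown beside them, and the conclusion is the same.
- **Fast heating at shallow depths alone does not trigger the 4°C stop.** Correct: that stop is set by the slowest depth and the 45°C stop by the fastest. Both remove subjects because of their temperature.
- **The target is undeclared.** Bias is measured against a 15-minute mean had nobody stopped, which step 10.a prevents for some subjects, and the SAP does not define this target. This stands, and the SAP should state what its 15-minute mean represents. The loss of observed 5- and 10-minute data does not depend on it.
- **A handling sentence and counts would be enough.** They would close the documentation gap. They would not remove the selection if the rule chosen were to analyse completers only.

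**Conclusion.** The concern holds. The Protocol lets the outcome end the measurement, and the SAP's only test presumes that measurement always reaches 15 minutes. One early stop is enough to force a decision that the SAP does not contain.

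The effect on the estimates is unknown. If 2.5 cm heats well below 0.267 °C/min, no depth nears 45°C and pain or discomfort stops are rare, it is negligible. If the mean 15-minute rise at 2.5 cm is near 4°C, roughly 9 to 12 of 25 subjects (25 − 15.9 and 25 − 13.1) would be lost. The completers' mean there would be about 0.6 to 0.7°C low, under linear heating with an SD of 1.0°C and correlation 0.6. Under the 4°C stop the bias at the slowest depth is downward. At the other depths, and for the depth differences, it can go either way. This should be settled in the SAP before data are seen.

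**What to change.** Leave the stopping rules unchanged and amend the SAP to:

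1. State that early-stopped subjects stay in the analysis.
2. Replace the complete-case ANOVA with a mixed model for rise from the subject's own baseline, using all temperatures recorded up to termination. Include depth × time with a curved time term (the quadratic was the form checked) and random slopes for subject and subject-by-depth.
3. Define each depth's rate over the subject's own treatment time, or derive it from the model.
4. Report how many subjects stopped before 5, 10 and 15 minutes, with reasons.

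The cost is a few sentences and a slightly longer analysis, with no new data: step 6 already records temperatures electronically. Recording only every 5 minutes and at termination also worked in the check (4.02 with linear and 4.10 with flattening heating, correlation 0.6, truth 4.00).

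The remedy has limits:

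- Fifteen-minute means for early-stopped subjects depend on the assumed curve. With flattening heating the quadratic model was off by up to +0.10°C at 2.5 cm and −0.13°C in the depth gap.
- Raw 10-minute means remain selected if anyone stops before 10 minutes.
- If heating flattens, rates over own treatment time cover different durations in different subjects.
- Pain or discomfort stops need a missing-at-random assumption that the data cannot verify.
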